- An *uncomplicated* vaginal delivery or planned cesarean section *expected* to occur in a hospital setting should NOT be reported as an AE, MAE or SAE.
- A medical *complication* that requires a cesarean section or an emergency induction may be reported as an SAE/AESI (as applicable), using the corresponding Expedited AE report form.

8.4.8.2. Reporting of congenital anomalies in relation to pregnancy outcomes and SAEs and/or AESIs

Table 9 summarizes the requirements for AESI/SAE reporting of adverse pregnancy outcomes when congenital anomalies are/are not present.

Table 9 Reporting pregnancy outcomes with or without congenital anomalies as AESIs and/or SAEs

	Live birth		Fetal death /stillbirth		Elective / Therapeutic Termination	
	AESI	SAE	AESI	SAE	AESI	SAE
None	-	-	-	X	-	X
Major ¹	X	if reportable per MACDP ³	-	X	-	X
Minor ²	-	if reportable per MACDP ³	-	X	-	X

* In the event of infant's participation in the study, congenital anomalies are to be reported in the infant's eCRF.

However, when there is no live birth, or no signed informed consent for the infant or the congenital anomaly is being reported for a subsequent pregnancy, it will be encoded in the maternal participant's eCRF.

¹Structural or functional defects that require surgical and/or medical treatment and that have serious adverse effects on health or development (functional) or have significant cosmetic impact.

²Anatomic variants or defects that do not have serious medical, functional or cosmetic consequences for the child.

³Metropolitan Atlanta Congenital Defects Program (MACDP) 6-Digit Code Defect List

Additional guidance when congenital anomalies are present are as follows:

The term “congenital anomaly” is broad. GSK uses the case definitions provided in the Centers for Disease Control and Prevention (CDC) Metropolitan Atlanta Congenital Defects Program guidelines, with specific reference to the MACDP 6-Digit Code Defect List [MACDP, 2021] to ensure that the collection and recording of these data is complete and consistent across studies and projects.

To report a pregnancy outcome of live birth with congenital anomaly as an SAE per these guidelines, an infant must have a birth defect that is *included in MACDP surveillance data* per the MACDP 6-Digit Code Defect List. (Congenital anomalies that are not included in MACDP surveillance data may be reported as medically attended or serious adverse events, if appropriate).

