The characterization of major and minor congenital anomalies will follow CDC definitions [CDC, 2019]. Major congenital anomalies are structural or functional defects that require surgical and/or medical treatment and that have serious adverse effects on health or development (functional) or have significant cosmetic impact. They are always reported as AESIs, even if they are not reportable as SAEs.

Minor congenital anomalies are anatomic variants or defects that do not have serious medical, functional or cosmetic consequences for the child. Minor congenital anomalies are not to be reported as AESIs, even if they are reportable as SAEs.

If minor congenital anomalies are *not* reportable *as per MACDP*, they should be recorded on the infant *AE eCRF*. ***Whether the event was medically attended or not should also be recorded in the infant AE eCRF. If they are not medically attended, they should be reported in the infant AE eCRF as medically attended event category “none”.***

For example:

- Cleft palate is a major congenital anomaly and should be reported as an AESI. Per the MACDP 6 Digit Code Defect list, cleft palate is always included in MACDP surveillance data and should therefore also be reported as an SAE.
- If congenital aortic valve insufficiency or regurgitation meets the criteria for a major congenital anomaly, it is an AESI. Per the MACDP 6-digit code list, congenital aortic valve insufficiency or regurgitation is only included in MACDP surveillance data and should only be reported as an SAE if designated as moderate or severe, or (if the degree is not specified) if another heart defect is present. Other cases could be reported as medically attended or serious adverse events if the infant meets any other protocol criterion for a medically attended or serious AE because of the condition.
- Mongolian spots, in the absence of any associated findings represent a minor congenital anomaly. Per the MACDP 6-digit code list, they are never included in MACDP surveillance data. They are neither an AESI nor an SAE. They do not typically satisfy the criteria for a medically attended AE and so, in general, would only be recorded *on the infant AE eCRF*.

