10.5.2. METHODS OF GESTATIONAL AGE ASSESSMENT AND ESTIMATION OF DUE DATE

Adapted from: The American College of Obstetricians and Gynecologists (ACOG) Committee on Obstetric Practice, American Institute of Ultrasound in Medicine and Society for Maternal-Fetal. Committee Opinions: Method for estimating Due Date. Number 700, May 2017 (accessed on-line on 05/Mar/2020 at: <https://www.acog.org/clinical/clinical-guidance/committee-opinion/articles/2017/05/methods-for-estimating-the-due-date>).

Gestational age range	Method of measurement	Discrepancy between U/S dating and LMP (or IUI or ET dating) prompting re-dating of EDD considering U/S
1 st trimester ≤13 ^{6/7} weeks		
≤8 ^{6/7} weeks 9 ^{0/7} to 13 ^{6/7} weeks	CRL	> 5 days > 7 days
2 nd trimester 14 ^{0/7} to 27 ^{6/7} weeks		
14 ^{0/7} to 15 ^{6/7} weeks	BPD, HC, AC, FL	> 7 days
16 ^{0/7} to 21 ^{6/7} weeks		> 10 days
22 ^{0/7} to 27 ^{6/7} weeks		> 14 days
3 rd trimester		
28 ^{0/7} weeks and beyond	BPD, HC, AC, FL	> 21 days

U/S: ultrasound examination; LMP: last menstrual period; IUI: intrauterine insemination; ET: embryo transfer; CRL: crown-rump length; BPD: biparietal diameter; HC: head circumference; AC: abdominal circumference; FL: femur length; , EDD: estimated date of delivery

* Based on LMP (or, if applicable, IUI/ET date)

10.6. Appendix 6: Definitions of maternal, fetal and neonatal events of interest as per GAIA

- Section 8.4.5.1 lists events of interest per GAIA that must be reported as AESIs.
- Other GAIA events of interest that meet the SAE definition should be reported with enough detail in the SAE narrative to permit level of diagnostic certainty assessment by GAIA criteria.
- Articles that discuss GAIA events of interest in detail can be found in the following issues of *Vaccine* [[Bauwens, 2016](#); [Jones, 2016a](#); [Jones, 2016b](#); [Kochhar, 2017](#)]:

- *Jones CE, Munoz FM, Spiegel HM, et. al. Guideline for collection, analysis and presentation of safety data in clinical trials of vaccines in pregnant women. Vaccine. 2016a;34(49):5998-6006.*

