4	
(Insufficient evidence to confirm)
 
Alterations in internal anatomy present:
 
 at the time of live birth and persistent beyond the immediate peripartum period unless surgically repaired OR at time of stillbirth, spontaneous abortion, or induced abortion 
AND
 
Confirmed:
 
 through medical record review, with the medical record demonstrating that the anomaly was present at the time of live birth or time of fetal demise, and that the anomaly was diagnosed by a trained maternal or child health care provider with minimal experience diagnosing congenital anomalies OR by claims data (ICD-9/ICD-10 diagnoses)

Functional Defects	
Level	Description
1	
For live births, alterations in functioning of one or more organs or body parts not due to a structural defect, present at the time of birth (or propensity to develop alteration present at live birth), and persistent beyond the immediate peripartum period, unless treated through gene therapy or stem cell transplantation
 
OR
 
For stillbirths, spontaneous or therapeutic abortions, alterations in functioning of one or more organs or body parts, not due to a structural defect
 
AND
 
Confirmed by definitive diagnostic study

2	
For live births, alterations in functioning of one or more organs or body parts not due to a structural defect, present at livebirth (or propensity to develop alteration present at live birth), and persistent beyond the immediate peripartum period, unless treated through gene therapy or stem cell transplantation
 
OR
 
For stillbirths, spontaneous or therapeutic abortions, alterations in functioning of one or more organs or body parts, not due to a structural defect
 
AND
 
Confirmed by documentation of a diagnosis made by a clinician experienced in diagnosing congenital anomalies and with the highest level of training in the diagnosis of functional defects for the specific setting

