3. ANALYSIS SETS

Table 2 Maternal Participants

| Analysis Set | Definition / Criteria | Analyses Evaluated |
|-------------------------|---|---------------------------------------|
| Screened | All participants who were screened for eligibility. | Study Population |
| Enrolled | All maternal subjects who completed the informed consent process and signed the informed consent form and were determined eligible for study participation. Note screening failures (who never passed screening even if rescreened) are excluded from the Enrolled analysis set as they did not enter the study. | Study Population |
| Full Analysis Set (FAS) | All maternal subjects who had pregnancy defined by this study (defined in the Protocol Section 5.1). | Primary, Secondary and other analyses |

Table 3 Infant Participants

| Analysis Set | Definition / Criteria | Analyses Evaluated |
|-------------------------|--|---------------------------------------|
| Enrolled Infant | Infants live-born to the maternal set, whose parents/LARs completed the informed consent process and signed the informed consent form. | Study Population |
| Full Analysis Set (FAS) | All infant subjects in the infant set who have post-delivery/birth data. | Primary, Secondary and other analyses |

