4.2.1. Definition of primary endpoints

The first pregnancy during study period is defined as the first pregnancy conceived post-vaccination or control in participants enrolled in RSV MAT studies (those previously received RSVPreF3 or control) up to Day 42 post-delivery.

Pregnancy outcomes include (not limited to):

1. Live birth
2. Spontaneous abortion

3. Stillbirth
4. Elective/therapeutic termination
5. Live birth Congenital anomaly(ies)
6. Spontaneous abortion Congenital anomaly(ies)
7. Fetal death/still birth Congenital anomaly(ies)
8. Elective/therapeutic termination Congenital anomaly(ies)

| Pregnancy-related AESIs | Infant AESIs |
|---|--|
| 
 • Hypertensive disorders of pregnancy: 
 – gestational hypertension, – pre-eclampsia, – pre-eclampsia with severe features including eclampsia; • Fetal growth restriction; • Pathways to preterm birth: 
 – premature preterm rupture of membranes, – preterm labor, – insufficient cervix – provider-initiated preterm birth; • Gestational diabetes mellitus; and • Chorioamnionitis. | 
 • Small for gestational age, • Low birth weight including very low and extremely low birth weight (<2500 g, <1500 g, <1000 g), • Congenital anomalies: 
 – major external structural defects, – internal structural defects, – functional defects, • Neonatal death 
 – in a non-viable live birth [<22 weeks gestation] – in an extremely pre-term birth [22.GA<28 weeks], – in a preterm live birth [28.GA<37 weeks], – in a term live birth, • Preterm birth |

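### The protocol conflicts with itself on whether a major congenital anomaly in a stillbirth or termination is an AESI, and no visible output counts major anomalies by arm across all pregnancy outcomes

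*Protocol*

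**What the plan says.** **Reporting rule.** The text of Protocol 8.4.8.2 says of major anomalies: "They are always reported as AESIs, even if they are not reportable as SAEs". It states no limit to live births. Table 9 in that section "summarizes the requirements for AESI/SAE reporting of adverse pregnancy outcomes when congenital anomalies are/are not present". Its row for major anomalies reads "Major ¹ X if reportable per MACDP ³ - X - X": AESI for a live birth, a dash under AESI for fetal death/stillbirth and for termination, and SAE for both kinds of loss. There is no column for spontaneous abortion.

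**Case definition.** Appendix 6 (Protocol 10.6) opens with "Section 8.4.5.1 lists events of interest per GAIA that must be reported as AESIs". Congenital anomalies are on that list, as infant AESIs. The Appendix 6 index flags several events as not being study AESIs; congenital anomalies carry no such flag and point to Table 29. Table 29 covers losses, for example under functional defects: "For stillbirths, spontaneous or therapeutic abortions, alterations in functioning of one or more organs or body parts, not due to a structural defect".

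**Data capture.** The note to Table 9 says that, when there is no live birth or no signed infant consent, the anomaly is still recorded: "it will be encoded in the maternal participant's eCRF".

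**Analysis.** SAP Table 3 defines the infant set as "Infants live-born to the maternal set, whose parents/LARs completed the informed consent process". SAP 4.2.2 counts infant AESIs per infant, from medical records only. SAP 4.2.1 also lists anomalies as pregnancy outcomes: categories 5 to 8 cover live birth, spontaneous abortion, fetal death/stillbirth and termination (the last as "Elective/therapeutic termination Congenital anomaly(ies"). SAP 4.2.2 counts these per pregnancy in the maternal Full Analysis Set. None of the four is divided into major and minor.

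**The concern.** Two things follow.

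First, the AESI status of the same case depends on which part of the protocol a site follows. For a termination with a major fetal anomaly, the 8.4.8.2 sentence and Appendix 6 point to an AESI, and Table 9 points to an SAE only. If such a case is filed as an AESI, it has no place in the infant AESI table, which holds live-born infants.

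Second, the one analysis that isolates major anomalies is conditional on live birth and infant consent. The other anomaly counts mix major and minor. Whether a pregnancy with a major anomaly reaches live birth is itself an outcome after vaccination. A comparison of arms among live births alone therefore cannot separate how often major anomalies occur from how often affected pregnancies continue. The study follows up a pregnancy-related safety signal, and its primary objective is to describe these events by arm. A rare event spread over tables with different units and definitions is hard to describe.

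**Working it through.** **1. The passages side by side, for a major anomaly**

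| Pregnancy outcome | 8.4.8.2 text | Table 9, AESI | Table 29 definition | Infant AESI rate | SAP 4.2.1 outcome category |
|---|---|---|---|---|---|
| Live birth, infant consented | AESI | Yes | Covered | Counted | 5, no major/minor split |
| Live birth, no infant consent | AESI | Yes | Covered | Not counted | 5, no split |
| Spontaneous abortion | AESI | No column | Covered | Not counted | 6, no split |
| Fetal death/stillbirth | AESI | No | Covered | Not counted | 7, no split |
| Termination | AESI | No | Covered | Not counted | 8, no split |

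The text and Table 9 disagree in two of Table 9's three outcome columns. Spontaneous abortion, which the SAP does list, is not addressed by Table 9.

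**2. Can the total be rebuilt from the planned rows?** The infant AESI row counts major anomalies per infant. Categories 6 to 8 count any anomaly per pregnancy. Adding them mixes units and adds minor anomalies in losses to major anomalies in live births. Categories 5 to 8 together give roughly the pregnancies with any anomaly, but not those with a major one. The outputs for the safety review team in SAP 6.3 also keep neonatal AESIs and pregnancy outcomes apart.

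**3. Does the live-birth restriction fix the direction of a difference?** The documents give no anomaly rate, so this step is an illustration only. For scale, Protocol 9.5 expects about 650 participants with a pregnancy. Its inputs give 2540 × 0.10 × 0.60 = 152.4 and 5700 × 0.50 × 0.30 × 0.60 = 513.0, together 665.4, which agrees with the rounded figure.

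Assumptions, not in the documents: singletons; 15% of pregnancies without a live birth, so 650 × 0.85 ≈ 552 live births; a major anomaly in 3% of live births, so about 17.

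- Live-birth rate: 17/552 = 3.1% (Clopper-Pearson 95% CI 1.8 to 4.9).
- All-pregnancy rate, by the share of affected pregnancies that end in loss:
  - 0%: 17/650 = 2.6%
  - 10%: (17 + 2)/650 = 2.9%
  - 20%: (17 + 4)/650 = 3.2%
  - 30%: (17 + 7)/650 = 3.7%

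The all-pregnancy rate exceeds the live-birth rate only when the share of affected pregnancies lost is larger than the share of all pregnancies lost (here 15%). Both numerator and denominator change, so the sign is open. Over assumed loss shares of 10 to 20%, live-born anomaly rates of 2 to 3% and the same 0 to 30%, the all-pregnancy rate runs from 1.5% to 4.0%.

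**The case against.** The best defence is that the 8.4.8.2 sentence was meant for live births. Its second half allows for a major anomaly that is not an SAE, which under Table 9 can happen only in a live birth. The preceding paragraph is about live births, 8.4.5.1 lists anomalies as infant AESIs, and 8.4.4 collects infant AESIs from birth. Table 9 also answers the stillbirth and termination cases explicitly. This reading is plausible, but the sentence does not say so, and it leaves Appendix 6 unresolved.

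The practical effect on expedited reporting is small: stillbirths and terminations are SAEs, and Protocol Table 7 gives SAEs and AESIs the same 24 hours. That stands.

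A reader might infer that fetuses lost with an anomaly disappear from the primary analysis. The documents do not support that. SAP categories 6 to 8 count them by arm with exact CIs, and SAEs are tabulated by arm under SAP 4.5.1. They are missing only from the major-anomaly AESI rate.

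Two cautions also stand. Parts of SAP 4.2.2, 4.3.1.2, 4.4, 4.6.1 and 4.6.2 are blacked out, so a combined table may be planned there. And the protocol describes no major/minor field for losses, so the availability of that item has to be confirmed.

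**Conclusion.** The point holds in a limited form. The protocol gives conflicting AESI rules for a major anomaly without a live birth; this rests on the text alone and no redaction affects it. The major-anomaly AESI percentage is restricted to live-born, consented infants. No visible output gives major anomalies by arm over all pregnancies; that part is subject to the redactions.

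No bias in the rate can be quantified. A reader might assume that 3% of 650 pregnancies (19.5) carry a major anomaly and that 20 to 40% of these are not live-born. That leaves 15.6 to 11.7 live-born cases and, over 650, suggests 2.4% to 1.8% and an understatement of one fifth to two fifths. That calculation divides live-birth cases by all pregnancies, whereas the SAP percentage is per live-born infant. With about 552 live births the same cases give 2.8% to 2.1%, and other inputs put the live-birth rate above the all-pregnancy rate. What such assumptions do show is a count: about 4 to 8 affected pregnancies would lie outside the AESI row. The inputs are not in the documents.

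The correction should be made, but the primary analysis is not invalid without it.

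**What to change.** **Protocol.** Reconcile the 8.4.8.2 text, Table 9 and Appendix 6 (including Table 29) so that one AESI rule applies to each pregnancy outcome, and state how Table 9 applies to spontaneous abortion. If data collection is complete by then, settle the rule as a classification for analysis and document it before the final analysis.

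**SAP 4.2.1, 4.2.2 and 4.3.1.2.** Split outcome categories 5 to 8 into major and minor. Add one row by arm with exact 95% CI: pregnancies with at least one major congenital anomaly in any outcome (live birth, spontaneous abortion, stillbirth, termination), each pregnancy counted once, over all study pregnancies with known outcome and medical records. Keep the live-birth infant AESI row beside it.

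**Cost.** A protocol clarification and one derived row. Anomalies in losses are already recorded in the maternal eCRF; confirm that major/minor status is recorded or can be assigned from the record. The drawback is that anomalies are less well ascertained in early losses, which can pull the all-pregnancy rate down. Show the GAIA certainty level for each case and report the row by outcome as well as in total, so that the reader can see where ascertainment is weak.

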8.4.9. Treatment of adverse events

- Any medication administered for the treatment of an SAE/AESI should be recorded *on* the Expedited Adverse Event Report of the participant's eCRF screen.

8.4.10. Covid-19 Infection

Maternal and infant COVID-19 cases identified during the study (as per standard of care) will be captured and reported using standard medically attended AE or SAE criteria, as outlined in Section 10.2. Additionally, all reported COVID-19 infections during a study pregnancy will be captured and reported on a COVID-19 screen of the eCRF.

COVID-19 cases should be reported in the eCRF according to the WHO Case Definition [[WHO, 2022](#)] using one of the following terms:

- Suspected COVID-19 infection
- Probable COVID-19 infection
- Confirmed COVID-19 infection.

8.5. Pharmacokinetics

PK is not evaluated in this study.

8.6. Pharmacodynamics

PD is not evaluated in this study.

8.7. Genetics

Genetics are not evaluated in this study.

8.8. Biomarkers

Biomarkers are not evaluated in this study.

8.9. Immunogenicity assessments

Not applicable for this study.

8.10. Health economics or medical resource utilization and health economics

Not applicable for this study.

9. STATISTICAL CONSIDERATIONS

The statistical analysis plan will be finalized prior to database lock and it will include a more technical and detailed description of the statistical analyses described in this section. This section is a summary of the planned statistical analyses of the most important endpoints including primary and key secondary endpoints.

9.1. Statistical hypotheses

This study is descriptive without statistical hypotheses. The primary and secondary objectives, as outlined in Section 3, are planned to be addressed using descriptive statistics.

9.2. Analysis sets

Table 10 Maternal Participants

Analysis Set	Definition / Criteria
Screened	All participants who were screened for eligibility.
Enrolled	All maternal subjects who completed the informed consent process and signed the informed consent form and were determined eligible for study participation. Note screening failures (who never passed screening even if rescreened) are excluded from the Enrolled analysis set as they did not enter the study.
Full Analysis Set (FAS)	All maternal subjects who had pregnancy defined by this study (defined in Section 5.1).

Table 11 Infant Participants

Analysis Set	Definition / Criteria
Enrolled Infant	Infants live born to the maternal set, whose parents/LARs completed the informed consent process and signed the informed consent form.
Full Analysis Set (FAS)	All infant subjects in the infant set who have post-delivery/birth data.

9.3. Statistical analyses

9.3.1. General considerations

All statistical analyses are descriptive. Besides the primary analyses, sub-group analyses may be conducted.

All primary and secondary analyses will be performed on the ***Full Analysis Set***.

9.3.2. **Primary endpoints analysis**

	Primary Endpoints	Statistical Analysis Methods
Maternal participants	Number and percentage of maternal participants reporting pregnancy outcomes and pregnancy related AESIs within the first pregnancy conceived within 2 years post-vaccination in participants enrolled in prior RSV MAT studies up to Day 42 post-delivery.	The number and percentage of maternal participants reporting pregnancy outcomes and pregnancy related AESIs within the first pregnancy conceived within 2 years post-vaccine/control will be tabulated with its exact 95% CI by study arms. By participant listings of pregnancy related outcomes and AESIs will be prepared
Infant participants	Number and percentage of infant participant reporting infant AESIs from the first pregnancy conceived within 2 years post-vaccination in participants enrolled in prior RSV MAT studies up to Day 42 post-delivery.	The Number and percentage of infant participant reporting infant AESIs from the first study pregnancy conceived within 2 years post-vaccine/control will be tabulated with its exact 95% CI by study arms. By participant listings of infant AESIs will be prepared.

Pregnancy outcomes include (not limited to) spontaneous abortion, stillbirth, and preterm birth. The pregnancy related adverse events of special interest (AESIs) and infant AESIs are listed in Section 8.4.5.1.

9.3.3. **Secondary endpoints analyses**9.3.3.1. **Pregnancy outcomes and AESIs from any study pregnancy**

	Secondary Endpoints	Statistical Analysis Methods
Maternal participants	Number and percentage of maternal participants reporting pregnancy outcomes and pregnancy related AESIs during any study pregnancy conceived within 2 years post-vaccination in participants enrolled in prior RSV MAT studies up to Day 42 post-delivery.	The number and percentage of maternal participants reporting pregnancy outcomes and pregnancy related AESIs during any pregnancy conceived within 2 years post-vaccination in participants enrolled in prior RSV MAT studies up to Day 42 post-delivery , will be tabulated with its exact 95% CI by study arms on subject level. By participant listings of pregnancy related outcomes and AESIs will be prepared.
Infant participants	Number and percentage of infant participant reporting infant AESIs from any study pregnancy conceived within 2 years post-vaccination in participants enrolled in prior RSV MAT studies up to Day 42 post-delivery.	The Number and percentage of infant participant reporting infant AESIs from any pregnancy conceived within 2 years post-vaccination in participants enrolled in prior RSV MAT studies up to Day 42 post-delivery , will be tabulated with its exact 95% CI by study arms on subject level. By participant listings of infant AESIs will be prepared.

9.3.3.2. **Selected pregnancy outcomes and AESIs by selected risk factors**

The number and percentage of selected pregnancy outcomes, pregnancy related AESIs and infant AESIs by study arms, stratified by selected risk factors, will be tabulated with exact 95% CIs for both first and any study pregnancy **conceived within 2 years post-vaccination in participants enrolled in prior RSV MAT studies up to Day 42 post-delivery.** Their relative risk estimates with 95% CIs and observed p-values will be reported for all comparisons accordingly.

Regarding preterm birth outcome, the comparisons will be conducted by study arms and by the combination of study arms and preterm birth history (Yes/No) in prior MAT study. The risk factors to be explored may include maternal smoking/household smoke exposure, maternal substance abuse, infections during pregnancy, COVID infection during pregnancy, prior preterm delivery, multiple gestation pregnancy, and short inter-pregnancy interval (less than 18 months between pregnancies), pregnancy complications such as preeclampsia and fetal distress.

